6.3.4 Evaluating Adverse Events

An investigator who is a qualified physician will evaluate all adverse events according to the NCI Common Terminology for Adverse Events (CTCAE), version 4.0. Any adverse event which changes CTCAE grade over the course of a given episode will have each change of grade recorded on the adverse event case report forms/worksheets.

All adverse events regardless of CTCAE grade must also be evaluated for seriousness.

Table 6 Evaluating Adverse Events

An investigator who is a qualified physician, will evaluate all adverse events as to:

V4.0 CTCAE Grading	Grade 1	Mild; asymptomatic or mild symptoms; clinical or diagnostic observations only; intervention not indicated.
	Grade 2	Moderate; minimal, local or noninvasive intervention indicated; limiting age-appropriate instrumental ADL.
	Grade 3	Severe or medically significant but not immediately life-threatening; hospitalization or prolongation of hospitalization indicated; disabling; limiting self-care ADL.
	Grade 4	Life threatening consequences; urgent intervention indicated.
	Grade 5	Death related to AE
Seriousness	A serious adverse event is any adverse event occurring at any dose or during any use of Merck product that:	
	†Results in death; or	
	†Is life threatening; or places the subject, in the view of the investigator, at immediate risk of death from the event as it occurred (Note: This does not include an adverse event that, had it occurred in a more severe form, might have caused death.); or	
	†Results in a persistent or significant disability/incapacity (substantial disruption of one's ability to conduct normal life functions); or	
	†Results in or prolongs an existing inpatient hospitalization (hospitalization is defined as an inpatient admission, regardless of length of stay, even if the hospitalization is a precautionary measure for continued observation. (Note: Hospitalization [including hospitalization for an elective procedure] for a preexisting condition which has not worsened does not constitute a serious adverse event.); or	
	†Is a congenital anomaly/birth defect (in offspring of subject taking the product regardless of time to diagnosis); or	
	Is a new cancer; (that is not a condition of the study) or	
	Is an overdose (whether accidental or intentional). Any adverse event associated with an overdose is considered a serious adverse event. An overdose that is not associated with an adverse event is considered a non-serious event of clinical interest and must be reported within 24 hours.	
	Other important medical events that may not result in death, not be life threatening, or not require hospitalization may be considered a serious adverse event when, based upon appropriate medical judgment, the event may jeopardize the subject and may require medical or surgical intervention to prevent one of the outcomes listed previously (designated above by a †).	
Duration	Record the start and stop dates of the adverse event. If less than 1 day, indicate the appropriate length of time and units	
Action taken	Did the adverse event cause the Merck product to be discontinued?	
Relationship to test drug	Did the Merck product cause the adverse event? The determination of the likelihood that the Merck product caused the adverse event will be provided by an investigator who is a qualified physician. The investigator's signed/dated initials on the source document or worksheet that supports the causality noted on the AE form, ensures that a medically qualified assessment of causality was done. This initialed document must be retained for the required regulatory time frame. The criteria below are intended as reference guidelines to assist the investigator in assessing the likelihood of a relationship between the test drug and the adverse event based upon the available information.	
	The following components are to be used to assess the relationship between the Merck product and the AE; the greater the correlation with the components and their respective elements (in number and/or intensity), the more likely the Merck product caused the adverse event (AE):	
	Exposure	Is there evidence that the subject was actually exposed to the Merck product such as: reliable history, acceptable compliance assessment (pill count, diary, etc.), expected pharmacologic effect, or measurement of drug/metabolite in bodily specimen?
	Time Course	Did the AE follow in a reasonable temporal sequence from administration of the Merck product? Is the time of onset of the AE compatible with a drug-induced effect (applies to trials with investigational medicinal product)?
	Likely Cause	Is the AE not reasonably explained by another etiology such as underlying disease, other drug(s)/vaccine(s), or other host or environmental factors

Relationship to Merck product (continued)		The following components are to be used to assess the relationship between the test drug and the AE: (continued)	
	Dechallenge	
Was the Merck product discontinued or dose/exposure/frequency reduced? If yes, did the AE resolve or improve? If yes, this is a positive dechallenge. If no, this is a negative dechallenge.
 
(Note: This criterion is not applicable if: (1) the AE resulted in death or permanent disability; (2) the AE resolved/improved despite continuation of the Merck product; or (3) the trial is a single-dose drug trial); or (4) Merck product(s) is/are only used one time.)
	
	Rechallenge	
Was the subject re-exposed to the Merck product in this study? If yes, did the AE recur or worsen? If yes, this is a positive rechallenge. If no, this is a negative rechallenge.
 
(Note: This criterion is not applicable if: (1) the initial AE resulted in death or permanent disability, or (2) the trial is a single-dose drug trial); or (3) Merck product(s) is/are used only one time).
 
NOTE: IF A RECHALLENGE IS PLANNED FOR AN ADVERSE EVENT WHICH WAS SERIOUS AND WHICH MAY HAVE BEEN CAUSED BY THE MERCK PRODUCT, OR IF REEXPOSURE TO THE MERCK PRODUCT POSES ADDITIONAL POTENTIAL SIGNIFICANT RISK TO THE SUBJECT, THEN THE RECHALLENGE MUST BE APPROVED IN ADVANCE BY THE U.S. CLINICAL MONITOR AS PER DOSE MODIFICATION GUIDELINES IN THE PROTOCOL.
	
	Consistency with Trial Treatment Profile	Is the clinical/pathological presentation of the AE consistent with previous knowledge regarding the Merck product or drug class pharmacology or toxicology?	
The assessment of relationship will be reported on the case report forms /worksheets by an investigator who is a qualified physician according to his/her best clinical judgment, including consideration of the above elements.			
Record one of the following		Use the following scale of criteria as guidance (not all criteria must be present to be indicative of a Merck product relationship).	
Yes, there is a reasonable possibility of Merck product relationship.		There is evidence of exposure to the Merck product. The temporal sequence of the AE onset relative to the administration of the Merck product is reasonable. The AE is more likely explained by the Merck product than by another cause.	
No, there is not a reasonable possibility Merck product relationship		Subject did not receive the Merck product OR temporal sequence of the AE onset relative to administration of the Merck product is not reasonable OR there is another obvious cause of the AE. (Also entered for a subject with overdose without an associated AE.)	

6.3.5 Sponsor Responsibility for Reporting Adverse Events

All Adverse Events will be reported to regulatory authorities, IRB/IECs and investigators in accordance with all applicable global laws and regulations.

7.0 STATISTICAL ANALYSIS PLAN

7.1 Statistical Analysis Plan Summary

The primary objective of this phase II study is to determine the overall response rate in patients with squamous cell carcinoma of the head and neck who have residual disease following definitive radiation with or without systemic therapy. This will be a single arm study of 24 patients with Stage I-IVB HNSCC who have residual disease after being treated with definitive radiation with or without systemic therapy.

The expected rate of resolution of disease without any further therapy is thought to be approximately 10%. This is derived from the Princess Margaret Hospital experience of 493 patients undergoing definitive chemoradiation for head and neck SCC, approximately 50% had less than a complete response to chemoradiation therapy at 8-12 week post therapy assessment²⁶. An additional 33% achieved CR between weeks 12 and 24. Of patients taken to neck dissection with less than a complete response (CR) the rate of positive residual tumor cells within the neck was 35%. This is substantially higher than the rate of positive residual cells at neck dissection in patients who achieve a CR to initial therapy, which was 9%. Thus it is estimated, that approximately 10% of patients that would likely have had pathologic residual disease at the 8-12 week assessment will achieve pathologic CR by 24 weeks without any further intervention. This estimate is given by:

the percentage of patients achieving a CR between weeks 12 and 24 x (the rate of pathologic positivity in non CR patients – the rate of pathologic positivity in CR patients)

$$= 33\% \times (35\% - 9\%) = 8.7\%, \text{ or approximately } 10\%.$$

Thus, assuming a baseline response rate of 10% (based on the Princess Margaret experience discussed above) and an improvement in response rate to 27% after treatment of chemoradiation, we will have 81% power to detect this difference with 24 patients by exact one-sample binomial test at one-sided significance level of 0.10. If 27% or more of patients in the study develop a partial or complete response to pembrolizumab, this strategy will be deemed worth of further investigation.

The primary endpoint of this trial will be overall response rate and the secondary endpoint will be progression-free survival. We will use descriptive statistics to calculate frequency and proportion for the response rate to pembrolizumab. 95% confidence interval will also be provided. Exact binomial test will be used to compare the observed response rate versus historical control. For the secondary endpoint, we will use Kaplan-Meier estimator to present the progression-free survival.

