2.0 TRIAL DESIGN

2.1 Trial Design

[figure not shown]
This is a phase II study for patients with squamous cell carcinoma of the head and neck who have residual disease following definitive therapy with radiation (with or without systemic therapy). Patients must be diagnosed with biopsy-proven residual disease within 24 weeks of completion of radiation therapy with or without systemic therapy. Residual disease must be biopsy proven and can be either from lymph nodes in the neck, or from the primary tumor site. Prior to beginning study therapy patients are evaluated by an ENT to determine if they have disease amenable to surgical resection. Both resectable and unresectable patients will be eligible for participation in the study. Patients will have repeat scans after 4 cycles (12 weeks) of treatment or disease progression, whichever comes first. Scans after 2 cycles will be performed as clinically indicated.

Patients then receive four cycles of pembrolizumab at 200mg given every three weeks. Repeat imaging is performed after two cycles to ensure there is not progression of disease. Patients who were deemed resectable prior to being enrolled on the study who show clinical radiographic or clinical progression after two cycles of therapy will discontinue study drug and proceed to surgical resection. Patients deemed to have unresectable disease who have radiographic progression but have signs of clinical benefit can continue on the drug. Following completion of four cycles of therapy, a biopsy is performed, and patients are again evaluated by ENT surgery. Patients with disease considered amenable to surgery would go on to surgical

resection. Patients considered unresectable or who refuse surgery can continue pembrolizumab until time of progression or for 1 year.

The primary endpoint is the overall response rate. Secondary endpoints include change in PD-L1 expression from baseline, changes in key immune cells, and progression free survival.

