4.2.3 Rationale for Endpoints

4.2.3.1 Efficacy Endpoints

The proposed strategy of pembrolizumab in this poor prognosis group of patients with residual disease will be deemed a strategy worthy of further investigation if the overall response rate could be increased to 27%.

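### The 10% null does not follow from its stated derivation for patients with residual disease, the group the trial enrols

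*Combined protocol and SAP*

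**What the plan says.** Section 7.1, and Section 4.2.1 in nearly the same words, build the null from a series of 493 patients given definitive chemoradiation. About 50% had less than a complete response (CR) at 8-12 weeks. Then "An additional 33% achieved CR between weeks 12 and 24", with no statement of whom the 33% is a percentage. Among patients who went to neck dissection with less than a CR, "the rate of positive residual tumor cells within the neck was 35" per cent; for those with a CR it was 9%. From 33% x (35% - 9%), printed as 8.7%, the plan concludes that "approximately 10% of patients that would likely have had pathologic residual disease at the 8-12 week assessment will achieve pathologic CR by 24 weeks".

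That figure becomes the null. "assuming a baseline response rate of 10" per cent and a target of 27%, the plan claims 81% power with 24 patients by a one-sided exact binomial test at 0.10. The go rule is separate: "If 27% or more of patients in the study develop a partial or complete response to pembrolizumab", the strategy merits further study. Section 4.2.3.1 uses the same 27%.

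Every enrolled patient has residual disease on biopsy (Section 5.1.1, criteria 3 and 12). Section 2.1 adds: "Residual disease must be biopsy proven and can be either from lymph nodes in the neck, or from the primary tumor site".

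**The concern.** The sentence describes a rate among patients who have residual tumour. The formula gives a rate among a wider group, most of whom, on the plan's own 35%, had no residual tumour to clear. Numerator and denominator therefore belong to different groups, and the group named in the sentence is the one the trial enrols.

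This matters because 10% is the only comparator in the primary test of a single-arm trial. If the untreated background is not 10%, the nominal error rate is not the real one. A rejection could then be read as benefit beyond spontaneous resolution when the design has not established that. The mismatch goes beyond the denominator: the 35% concerns the neck only, the source outcome is pathologic CR, and the source window is weeks 8-12 to 24. The trial also takes primary-site disease, counts partial responses, and follows a different clock.

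**Working it through.** **1. The plan's own figures.** Inputs from Section 7.1: n = 24, null 0.10, alternative 0.27, one-sided 0.10. With P(X >= r) = sum over k >= r of C(24,k) p^k (1-p)^(24-k):

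- P(X >= 4 | 0.10) = 0.214 and P(X >= 5 | 0.10) = 0.085, so the cutoff is 5/24 with exact alpha 0.085.
- P(X >= 5 | 0.27) = 0.817, which reproduces the stated 81%.
- The go rule needs 0.27 x 24 = 6.48, hence at least 7/24. P(X >= 7 | 0.10) = 0.0075.
- The product is 0.33 x 0.26 = 0.0858, so 8.6% rather than 8.7%. The slip is immaterial in itself.

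**2. The rate for the group named, if the 33% is of incomplete responders.** Take 1,000 incomplete responders.

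- With residual tumour: 0.35 x 1,000 = 350. Without: 650.
- Late converters: 330. Positive before conversion, applying 35% to them as the plan does: 115.5. Positive after, at 9%: 29.7.
- Cleared: 115.5 - 29.7 = 85.8.
- Share of the whole group: 85.8/1,000 = 8.58%, the plan's figure. Share of those with residual tumour: 85.8/350 = 24.5%.

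**3. The same, if the 33% is of all patients.** Per 1,000 patients, 500 are incomplete responders and 175 have residual tumour. Cleared: 330 x 0.26 = 85.8. Rate: 85.8/175 = 49.0%.

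Adding residual disease in initial complete responders to the denominator (0.5 x 35% + 0.5 x 9% = 22%) gives 0.5 x 8.58/22 = 19.5% and 8.58/22 = 39.0% on the two bases.

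**4. How far this depends on applying 35% to late converters.** The documents do not give positivity in late converters; call it q. On the incomplete-responder base:

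- If 35% is the average over all incomplete responders, the rate is 0.33(q - 0.09)/0.35.
- If 35% describes those who stayed non-CR, it is 0.33(q - 0.09)/(0.33q + 0.67 x 0.35).

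| Assumed q | First reading | Second reading |
|---|---|---|
| 35% | 24.5% | 24.5% |
| 25% | 15.1% | 16.7% |
| 20% | 10.4% | 12.1% |
| 15% | 5.7% | 7.0% |

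On the all-patients base with q = 15%, the first reading gives 0.66 x 0.06/0.35 = 11.3%. So the inputs can give a rate on either side of 10%, depending on a quantity the plan does not supply.

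**5. What the decision rules do if the background is not 10% and the drug has no effect.**

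| True background | P(at least 5/24) | P(at least 7/24) |
|---|---|---|
| 10% | 0.085 | 0.0075 |
| 15% | 0.287 | 0.057 |
| 20% | 0.540 | 0.189 |
| 24.5% (illustration) | 0.736 | 0.371 |

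P(X >= 5) reaches 0.10 at a background of 10.5%; P(X >= 7) reaches it at about 17.0%.

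**6. Window and endpoint.** Section 5.1.1 (criterion 11) allows the confirming biopsy at 6 to 24 weeks and the first dose up to 28 weeks after radiation. Section 6.2.2.12.1 scores response from the last pre-drug scan. Four three-week cycles take 12 weeks, so the response scan could fall as early as about week 18 (6 + 12), inside the source window, or as late as about week 40 (28 + 12), well after it. Late entry could lower the background; counting partial responses would raise it. The documents quantify neither.

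**The case against.** The strongest reply is that 24.5% is no better founded than 10%. It needs late converters to have been 35% positive, yet that figure comes from patients taken to neck dissection with less than a CR, at a time the plan does not give. Patients about to convert may well have had less viable tumour; at 15% the rate falls to about 6-7% on the incomplete-responder base. The 49% rests on an unstated denominator. For late enrolees the source window is largely over. All of this stands. The documents fix neither the size nor the direction of the error in the true background.

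A reader might therefore go too far and infer that the real null is 24.5% or 49%, that the test has a 74% false-positive rate, or that the design cannot succeed: at a 24.5% null the cutoff would be 10/24, with 8.6% power at 27%. The documents do not support this, because each of those figures carries the unproven 35% into a different time window and endpoint.

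It can also be said that Section 7.1 hedges, calling 10% estimated and assumed; that the 27% rule is stricter than the test; that "95% confidence interval will also be provided"; and that the declared consequence is only further investigation. This tempers the harm. It does not repair the derivation: the same section says the 10% is derived from the series, and that is the statement that fails. Applying 35% to late converters is also the plan's own step, so the plan cannot rely on it in the numerator and omit the matching denominator.

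**Conclusion.** The point holds as a fault in the derivation, and it should be fixed. It is certain that 33% x (35% - 9%) is not a rate among patients with residual disease, and that 10% does not follow from it for the enrolled group. The plan therefore has no derived background rate for its own population, time window and CR-plus-PR endpoint.

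The true background is not known. The 24.5% and 49% are what the plan's inputs yield once the denominator is supplied, assuming 35% positivity in late converters; they are not replacement nulls. The 0.736 and 0.371 at 24.5% are likewise illustrations.

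The power calculation is right given 10%. The practical weakness is the thin margin: the primary test holds its level only up to a 10.5% background, while the go rule tolerates about 17.0%. Rejecting 10% shows a response rate above 10%, and no more.

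**What to change.** Keep the sample size, the test and the go rule. In Sections 4.2.1 and 7.1:

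1. Correct the product to 8.6%. State the base of the 33% and when the 35% was measured.
2. Correct the denominator, or stop describing 10% as derived from the series for patients with residual disease.
3. Then choose one course. Either justify a null for the enrolled population, time window and CR-plus-PR endpoint, and recheck cutoff, power and n if it changes. Or label 10% an assumption and state that rejecting it shows only a response rate above 10%, not benefit beyond spontaneous resolution.
4. Add a short sensitivity statement giving the false-positive rates of 5/24 and 7/24 over a range of background rates, with the 10.5% and 17.0% crossings. Do not present any such range as the plausible background.

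Reporting CR separately and tabulating weeks from radiation to the pre-drug scan would help interpretation but are optional.

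The cost is wording and one small table, with no extra patients unless the sponsor adopts a higher null. The real price is a weaker supportable conclusion: a positive test could no longer be presented as exceeding spontaneous resolution.

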1. In the case that a patient initiates a subsequent anti-cancer therapy the 30 day follow up should occur prior to the first dose of the new therapy and patients will move to survival follow up.
2. Vital signs should include temperature, pulse, respiratory rate, weight and blood pressure. Height will be measured at screening only.
3. Vital signs will be taken prior to the administration of each dose of trial treatment and at discontinuation of each treatment.
4. ECOG status will be evaluated prior to the administration of each dose of trial treatment and at discontinuation of each treatment.
5. Screening lab will be assessed within 14 days of first treatment.
6. After cycle 1, pre-treatment labs can be drawn up to 72 hours pre-dose.
7. The baseline CT scan can be from before study enrollment as long as the scan is within 4 weeks of study treatment.
8. Archival tissue from a biopsy prior to radiation treatment with or without systemic therapy should be requested.
9. All patients will have a biopsy prior to the start of study treatment. This specimen may be obtained up to 6 weeks (42 days) prior to initiation of treatment on Day 1 and following completion of RT/CRT. This pre-treatment biopsy can be used to confirm residual disease.
10. Patients will have a research biopsy after completion of the 4th treatment cycle or at study discontinuation if they come off treatment before cycle 4. There will be no additional biopsy for patients who stay on treatment past 4 cycles.
11. Imaging during study treatment cycles will occur at the end of cycle 2 when clinically indicated and cycle 4 or at disease progression whichever comes first (required). Less frequent imaging is acceptable during the continuation cycles, although a minimum of every 8 weeks is recommended.
12. If a patient comes off trial for reasons other than disease progression imaging should be done every 9 weeks ±7 days
13. Information on SAEs will be collected for 90 days after the end of treatment. Any unexpected SAE that occurs more than 90 days after drug administration but is possibly, probably or definitely attributed to drug administration will be recorded and reported.
14. Patients will have a repeat ENT evaluation for resectability status after completion of the 4th treatment cycle or at study discontinuation if they come off treatment before cycle 4. There will be no additional ENT evaluation for patients who stay on treatment past 4 cycles

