6.2.2.12.1 Measurement of Response

Following pembrolizumab, response will be measured in comparison to the most immediate pre-pembrolizumab imaging study. For complete definitions of measurable and non-measurable disease, please refer to the RECIST v1.1 criteria.

1. For lesions that meet the criteria for measurable disease outlined in RECIST 1.1, the standard RECIST response criteria will apply

RECIST response criteria:

Complete response: Disappearance of all target lesions. Any pathological lymph nodes (whether target or non-target) must have reduction in short axis to <10 mm.

Partial response: At least a 30% decrease in the sum of diameters of target lesions, taking as reference the baseline sum diameters.

Progressive disease: At least a 20% increase in the sum of diameters of target lesions, taking as reference the smallest sum on study (this includes the baseline sum if that is the smallest on study). In addition to the relative increase of 20%, the sum must also

demonstrate an absolute increase of at least 5 mm. (Note: the appearance of one or more new lesions is also considered progression).

Stable disease: Neither sufficient shrinkage to qualify for PR nor sufficient increase to qualify for PD, taking as reference the smallest sum diameters while on study.

2. The following 2 criteria for evaluation of clinical response will apply for **lesions considered too small for measurement by RECIST 1.1** (for example nodes with short axis < 1.5cm or primary lesions or skin lesions < 1cm).

The lesion would have to shrink to < 1cm in all three dimensions and also have at least a 30% decrease in the sum of diameters of target lesions, taking as reference the baseline sum diameters.

AND

One of the following two criteria are true:

- 1) Either the biopsy performed after pembrolizumab shows no active cancer

OR

- 2) The patient has a PET scan after pembrolizumab which demonstrates that a previously active lesion (SUV \geq 3.0) is now PET negative (SUV < 3.0).

In the case where both PET and biopsy are both performed, and the results are disparate, the biopsy results will take precedence. For example a positive biopsy in this situation would connote a designation of response as a PR, and a negative biopsy would connote a response as a CR.

Response will be evaluated by imaging studies as described in the study calendar. If symptoms develop or clinical deterioration occurs, patients may be imaged prior to the pre-specified time points for imaging.

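### The 10% null is a pathologic complete-resolution rate with no partial responses in it, but the endpoint tested against it counts partial responses

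*Combined protocol and SAP*

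**What the plan says.** Section 7.1 (and section 4.2.1, in nearly the same words) builds the null from a cited chemoradiation series of 493 patients. About half had less than a complete response at 8 to 12 weeks. "An additional 33% achieved CR between weeks 12 and 24". At neck dissection, 35% of patients without a complete response had viable tumour, against 9% of those with one. The product 33% × (35% − 9%) is rounded to 10% and described as the share who "will achieve pathologic CR by 24 weeks without any further intervention".

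The power statement then carries this figure over as a response rate: "assuming a baseline response rate of 10% (based on the Princess Margaret experience discussed above"). The alternative is 27%, with 24 patients, an exact one-sample binomial test at one-sided 0.10, and a stated power of 81%. Section 7.1 confirms that the observed response rate will be compared with the historical control by an exact binomial test.

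The condition for pursuing the strategy is worded separately: "If 27% or more of patients in the study develop a partial or complete response to pembrolizumab". For measurable lesions, section 6.2.2.12.1 reads "Partial response: At least a 30% decrease in the sum of diameters of target lesions, taking as reference the baseline sum diameters". The baseline is the last scan before pembrolizumab, and no pathology is required.

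**The concern.** The control and the endpoint measure different outcomes. The inputs to the 10% are one complete-response percentage and two pathologic-positivity rates. An untreated patient whose measurable nodes shrink by 40% with viable tumour remaining adds nothing to the control, yet would be a responder in this trial.

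The population makes this more than a matter of labels. Section 4.2.1 acknowledges that response to chemoradiation can be slow. Inclusion criterion 11 allows the confirming biopsy from 6 weeks after radiation. A patient who starts soon after that and completes four three-week cycles is assessed at about week 6 + 12 = 18, inside the period in which the cited series saw further complete responses. There is no concurrent control, so the historical rate is the only protection against crediting the drug with late radiation effect. For this comparison the mismatch can act in one direction only, towards a positive result.

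**Working it through.** **Inputs.** From section 7.1: N = 24, p0 = 0.10, p1 = 0.27, one-sided α = 0.10, exact binomial test, and the 27% criterion. The documents give no untreated partial-response rate, so untreated partial-plus-complete rates of 12% to 25% are assumptions used to show sensitivity.

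**The null.** 0.33 × (0.35 − 0.09) = 0.0858, or 8.6% (section 7.1 prints 8.7%; the difference is immaterial), rounded to 10%. The rounding adds about 1.4 percentage points. The documents do not present it as an allowance for partial responses.

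**Reproducing the power.** With X ~ Binomial(24, p), the test needs the smallest r with P(X ≥ r | 0.10) ≤ 0.10.
- r = 4: 0.214, too large.
- r = 5: 0.085, so the test rejects at 5 or more (5/24 = 20.8%).
- Power: P(X ≥ 5 | 0.27) = 0.817, which agrees with the stated 81%.

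The arithmetic is sound. The question is what p0 measures.

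**The 27% criterion.** 0.27 × 24 = 6.48, so at least 7 responders are needed (7/24 = 29.2%). This is a stricter rule than the exact test. Its power at 27% is P(X ≥ 7 | 0.27) = 0.482; the stated 81% does not apply to it.

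**Chance that an inactive drug succeeds**, P(X ≥ r | p), where p is the untreated partial-plus-complete rate:

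| Untreated rate p | Exact test (≥ 5/24) | 27% rule (≥ 7/24) |
|---|---|---|
| 10% (plan) | 8.5% | 0.7% |
| 12% (assumed) | 15.3% | 1.9% |
| 15% (assumed) | 28.7% | 5.7% |
| 20% (assumed) | 54.0% | 18.9% |
| 25% (assumed) | 75.3% | 39.3% |

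Solving P(X ≥ r | p) = 0.10 for p gives 10.5% for r = 5 and 17.0% for r = 7. The exact test therefore has almost no room for untreated partial responses, while the 27% rule has some.

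**If the null were raised instead.** With 24 patients and α ≤ 0.10, p0 = 15% would need 7 responders (power at 27%: 48%) and p0 = 20% would need 8 (power 31%). Without a documented untreated rate, neither value can be justified.

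**The case against.** The mismatch itself is hard to dispute, but its size and its remedy can be challenged.

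*Size under the decision rule.* A reader might infer that the chance of wrongly declaring the strategy worth pursuing is 29% to 75%. The documents do not support that. Section 7.1 ties that declaration to 27% of patients, where the figures are 5.7% to 39.3% over the same assumed range. The larger figures describe rejection of the null by the exact test. Both rules appear in section 7.1, so both need to be shown.

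*Evidence for the assumed rates.* A reader might also take the 33% late complete responses as evidence of a high untreated rate here. It is not. In that series only 35% of patients with less than a complete response who went to neck dissection had viable tumour, whereas this trial requires biopsy-proven disease. Regression in a mostly pathology-negative group does not show how often biopsy-positive lesions shrink by 30%.

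*Design features that limit the bias.* These objections stand:
- The baseline CT must fall within 4 weeks of treatment, so shrinkage before it is not counted.
- The first dose may come as late as 28 weeks after radiation. Such a patient has a baseline scan no earlier than week 28 − 4 = 24 and falls outside the week 12 to 24 period.
- Measurable disease is not required. Lesions too small for RECIST need shrinkage plus a negative biopsy or PET conversion.

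None of these adds partial responses to the control, and the documents do not quantify their effect.

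*A tempting remedy.* Comparing all negative post-treatment biopsies with 10% may look like for like. It is not, because it would credit a negative needle biopsy in a patient without complete response on imaging, who is not in the 10%. Section 6.2.2.13.1 also lets the principal investigator waive the tissue requirement.

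**Conclusion.** The point holds. The null in section 7.1 is a complete-resolution rate and is not a valid reference for partial plus complete response. Exceeding 10% on that endpoint does not by itself show activity beyond delayed radiation response. The nominal 0.10 level of the exact test depends on an untreated partial-plus-complete rate of no more than about 10.5%, which the documents do not establish.

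The direction of the bias is clear, but its size is not. The 15% to 25% range is an assumption, and the true rate could be close to 10% if few biopsy-positive lesions shrink late. The documents do not support a claim that the trial's error rate is any particular inflated value. The sample-size calculation reproduces and is not in question.

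**What to change.** In section 7.1:

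1. State that the 10% is a pathologic complete-resolution rate containing no partial responses, and that exceeding it on partial plus complete response does not alone show activity beyond delayed radiation effect.
2. Keep partial plus complete response as the overall response rate, with its confidence interval.
3. Tabulate the false-positive rate of both success rules over an assumed untreated rate of 10% to 25%.
4. Pre-specify a further comparison with the 10% limited to complete responders: complete response on imaging with negative tissue, from the resection specimen if the patient is operated on and otherwise from the post-cycle-4 biopsy. Patients without complete response or without tissue count as not cleared.

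Footnote 10 of section 6.1 already plans for the tissue: "Patients will have a research biopsy after completion of the 4th treatment cycle or at study discontinuation if they come off treatment before cycle 4". Because the requirement can be waived, the missing-tissue rule in item 4 is needed.

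The cost is SAP wording and one more proportion, with no added patients or visits. The claim from the main test becomes narrower. The complete-response comparison also needs 5 of 24 and has less power: from the same binomial, 54% if the true cleared rate is 20% and 29% if it is 15%. Biopsy sampling is imperfect. The comparison comes closer to what the 10% measures but inherits any error in that estimate.
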